## 9.3 Populations for Analyses

E-Cigarette Users

## 9.4 Statistical Analyses

To account for the repeated Cmax (adjusted for baseline at time zero) assessments design and to evaluate the extent of within-subject correlation of Cmax outcomes, we will first compute using linear mixed effect models, the intra-class correlation coefficients for the Cmax measures, first separately for each of the forms (protonated and free base) and then for all Cmax measurements from the same participant. This step will help us understand the magnitude within-subject correlation of Cmax measures and to compare the within-subject correlation for the two main forms. Next, for each of the forms, we will investigate how Cmax relates to changing nicotine flux, by using linear mixed effect models (accounting for the within-subject design) and flux conditions as a predictor; we will investigate flux conditions both categorically and continuously to detect whether the change in Cmax follows a specific linear trend or whether some flux concentrations relate differently to Cmax. We will use model fit criteria to select the correlation structure and representation of flux concentrations that best describes the data. This investigation will be complemented by splines and locally weighted scatterplot smoothing (LOWESS) graphs to visualize plots of Cmax changes over the flux values. These analyses will be performed separately for the protonated and freebase conditions to assess similarities and differences in how the form of nicotine is influencing the Cmax-flux concentration relationship. Finally, we will integrate the form effect by using linear mixed models with both concentration and form as predictors as well as an interaction term between form\*concentration

to investigate whether different form-concentration combinations influence Cmax differently. The same sequence of analysis will be completed for the other outcomes of interest: dCi/dt, Tmax and AUC, to evaluate how the different fluxes and forms relate to rate of rise of nicotine, the time to Cmax and to cumulative nicotine exposure over time. We will investigate the relationship of participants' characteristics, such as sex, age, history of smoking, and baseline dependency scores with our pharmacokinetics outcomes. We will also look at whether some of these characteristics, namely sex, change the relationship between nicotine flux and the outcomes. In additional analysis, we will evaluate whether nicotine fluxes are related to changes in puffing intensity. We will also repeat the main analyses adjusting for puffing intensity.

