# 9 - Statistical Considerations

## 9.1 Statistical Hypotheses

We hypothesize that computed nicotine flux will predict the rate of nicotine rise and maximum nicotine concentration observed in arterial blood, and that protonated nicotine will result in higher delivery.

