#### **9.4.1 General Approach**

As above.

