#### **9.4.2 Analysis of the Primary Efficacy Endpoint(s)**

As above.

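### Unnamed fit criteria choose the flux coding from the outcome data and no flux test is named as primary; if the p-value comes from the selected per-form model, type I error is about 7–8% rather than 5%

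*Combined protocol and SAP*

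**What the plan says.** Section 9.1 gives the hypothesis that "computed nicotine flux will predict the rate of nicotine rise and maximum nicotine concentration observed in arterial blood", but no test. Section 9.2 sets alpha at 0.05 and claims 90% power with 15 participants, an ICC of 0.4 and an effect size of 0.4. It does not say whether the powered test is a slope, a comparison of four levels, or part of the two-form model.

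Section 9.4 then lays out a sequence for Cmax:

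- Within each form, "we will investigate flux conditions both categorically and continuously to detect whether the change in Cmax follows a specific linear trend", or whether particular levels behave differently.
- The choice between codings, and of the covariance, is left to the data: "We will use model fit criteria to select the correlation structure and representation of flux concentrations that best describes the data".
- "These analyses will be performed separately for the protonated and freebase conditions".
- "Finally, we will integrate the form effect by using linear mixed models with both concentration and form as predictors", plus their interaction. Nothing says which flux coding enters this model.
- "The same sequence of analysis will be completed for the other outcomes of interest: dCi/dt, Tmax and AUC".

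Section 9.4.2, where the primary analysis should be fixed, only refers back to this text, as does 9.4.1.

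**The concern.** The plan leaves three candidate flux tests (one per form and one joint), each with two possible codings. The rule for choosing the coding looks at the outcome that is then tested. A test run after such a choice does not keep its nominal level, because the selection tends to favour whichever coding happens to fit the noise. A reader also cannot tell in advance which result would count as confirming the hypothesis. At stake are the 5% error rate in 9.2 and the clarity of the claim that flux predicts delivery, which the Synopsis intends as evidence for regulators.

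**Working it through.** **Inputs from the plan.** Alpha 0.05, 15 participants, ICC 0.4, effect size 0.4 (9.2); four fluxes per form (6.1.2), so 15 × 4 = 60 Cmax values per form; linear and categorical codings (9.4).

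**Assumptions, because the plan is silent.** Effect size read as Cohen's f; two-sided or omnibus tests; complete data; random intercept unless stated; AIC, AICc, BIC and the likelihood-ratio test tried as fit criteria.

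**1. The plan's own figure.** Noncentrality λ = n·m·f²/(1 − ICC) = 15 × 4 × 0.16/0.6 = 16.

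- 3-df test, F(3, 42): power 90.8%. With 14 participants, λ = 14.93 and F(3, 39) gives 88.4%.
- Slope, F(1, 44): power 97.4%.

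The stated 90% with 15 participants therefore reproduces.

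**2. Type I error after selection, one form, no flux effect.** With a random intercept the within-participant variation splits into independent parts: L (linear contrast, χ² on 1 df), Q (the other two flux contrasts, 2 df) and E (error, 42 df). Then

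- F_lin = L / [(Q + E)/44]
- F_cat = [(L + Q)/3] / (E/42)
- categorical flux is selected if 45·ln[(Q + E)/E] exceeds the cut-off c.

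The p-value is taken from the selected model (2,000,000 draws):

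| Rule | c | Rejects at 0.05 |
|---|---|---|
| Linear or categorical, fixed in advance | – | 5.0% |
| AIC | 4 | 8.2% |
| AICc, n = 60 | 4.86 | 8.2% |
| BIC, n = 15 | 2 ln 15 = 5.42 | 8.1% |
| Likelihood-ratio test | 5.99 | 8.0% |
| BIC, n = 60 | 2 ln 60 = 8.19 | 7.1% |
| AICc, n = 15 | 10.5 | 5.7% |
| p < 0.05 in either coding counts | – | 8.2% |

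Other settings: AIC with an unstructured covariance among the candidates gives 8.9%. AIC with REML Wald chi-square tests gives 9.8%, although those tests already run at 5.7% and 6.4% with the coding fixed. Hence about 6–10% overall.

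**3. Form-by-flux interaction in the joint model.** Fixed coding gives 5.0%. The rest depends on an unstated carry-over rule: 5.0–5.9% if both forms must select categorical, 6.2–7.6% if one suffices, 5.1–7.7% if the coding is selected afresh (BIC to AIC).

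**4. Power under selection.** With a truly linear effect, 97.7% (AIC) and 97.5% (BIC), against 97.4% for the fixed slope. Selection costs no power there.

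**5. Would fixing the coding in a random-intercept model be enough?** I simulated the joint two-form model with zero mean flux effect, but with a linear flux response that varies between participants and is shared across forms. Its SD is an assumed fraction of the residual SD, because the documents give no figure.

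| SD ratio | Slope, random intercept | 3-df, random intercept | One-sample t test on per-participant slopes |
|---|---|---|---|
| 0 | 5.0% | 5.0% | 5.0% |
| 0.5 | 9.8% | 6.7% | 5.0% |
| 0.7 | 13.7% | 8.4% | 5.0% |

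**6. Power of tests that allow such differences**, evaluated when none exist:

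- Per form, λ = 16: t test on 15 per-participant slopes, F(1, 14), 96.0%; 3-df test with unstructured covariance, F(3, 12), 82.2%.
- Averaged over forms, λ = 15 × 8 × 0.16/0.6 = 32: 99.9% and 98.7% respectively.

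**The case against.** The strongest reply is that selection may serve description only. Section 9.4 says both codings are fitted to learn the shape of the relation, and it nowhere says that p-values come from the selected model. That stands: the error figures are conditional. A reader might infer that the planned flux test runs at 7–8%. The documents do not support that, because they do not say which model supplies the p-value.

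Second, type I error needs a null effect, and 9.2 anticipates a stronger flux–Cmax relation than the one powered for. This also stands for Cmax, where the main gain is clarity. It is weaker for Tmax: the same sequence is applied there, and with puff duration and interval held constant by design a null flux effect is plausible.

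Third, this is an Early Phase 1 mechanistic study. But the plan states a hypothesis, an alpha, a power and a primary-endpoint section, and marks exploratory analyses as not applicable. Saying which test carries the hypothesis is a modest request.

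Fourth, fixing one coding in a random-intercept model could leave an error rate as large as the one being removed (step 5). That is correct, and the fix below allows for it.

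**Conclusion.** The gap in the text is certain: an unnamed criterion selects the coding and covariance on the outcome data, and no flux test is designated. The consequence is moderate and conditional. If the p-value is taken from the selected per-form model and flux has no effect, type I error per form and outcome is about 7–8% with AIC or BIC, F tests and a random intercept, and about 6–10% across other criteria and tests. The effect on the interaction test is uncertain, at about 5–8%.

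Two further inferences should be resisted. The sample size is not in error, since 90.8% reproduces the stated 90%. Nor does that match show that 9.2 was based on a 3-df test per form: the effect-size metric and the test are not named, so this is only a consistent reading.

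**What to change.** In 9.4.2, before data are seen:

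- Name one primary flux test for baseline-corrected Cmax, the model that carries it, and whether it is per form or averaged over forms.
- Fix the coding, 3-df or slope. Either is defensible and the choice is the team's. Use the same coding for the form-by-flux interaction.
- Do not rely on a random intercept alone. Use a random flux slope, an unstructured covariance with small-sample df, or a one-sample test on per-participant slopes. Of these, the last was simulated here and held 5.0% throughout.
- Keep the other coding, fit-based selection with a named criterion (and its n), splines and LOWESS as secondary or descriptive. State the status of the remaining outcomes and of the form comparison.

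The cost is wording only; no visit, sample or planned analysis is lost. The statistical trade-offs are:

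- A 3-df test gives up power for a linear trend (90.8% against 97.4% per form at f = 0.4 with a random intercept).
- A slope can miss pure curvature (it rejects about 2% of the time).
- Allowing for differing responses costs df. Per form the slope falls from 97.4% to 96.0%, and the 3-df test with unstructured covariance from 90.8% to 82.2%. Power would be lower still if participants do differ.
- Averaging over forms loses power if only one form responds: at f = 0.4 in that form, λ = 8, giving 63.5% (3-df) or 80.0% (slope) with a random intercept. The secondary per-form and interaction tests would have to show that case.

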### **6.3 Measures to Minimize Bias: Randomization and Blinding**

The flux/form conditions will be tested by participants in two lab visits separated by one to four weeks to minimize carryover effects. All sessions will be double-blinded. In the first visit, participants will use the ENDS device with one nicotine form and four fluxes in random order. Participants will be instructed to attend the lab for a second visit, to test the four fluxes but with the other nicotine form (free base or protonated). The second visit will allow us to isolate the effect of nicotine form on nicotine delivery. The order of nicotine form in the two visits will be counter-balanced across participants.

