## 9.2 Sample Size Considerations

Assuming an alpha level of 0.05 and an ICC of 0.4 (which conservatively assumes only modest correlation between Cmax measures within the same participant), we estimated that we would need a total sample size of 15 subjects (completing two sessions) to detect with 90% power a medium effect size of 0.4. In the event of participant attrition, we will recruit additional participants to replace those lost to follow up and maintain statistical power. With an anticipated higher ICC and a higher relationship between flux and Cmax, as suggested by our prior work, this design will be well-powered to investigate the relationship of Cmax and flux concentrations for each form separately, and over 88% power to detect an effect size 0.4 for the between and within group comparisons [i.e., form\*concentration]. We will continue recruitment until we achieve the targeted sample size.

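### The pooled form model in 9.4 names no random effects; with participant-only clustering, the standard error of the flux-averaged form effect is too small if delivery varies between visits

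*Combined protocol and SAP*

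**What the plan says.** Sections 4.1 and 6.3 set out two visits, one to four weeks apart. Each visit uses one form and all four fluxes in random order, and form order is counter-balanced. Section 6.3 gives the purpose: "The second visit will allow us to isolate the effect of nicotine form on nicotine delivery". Section 9.1 includes the hypothesis that "protonated nicotine will result in higher delivery".

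Section 9.4 proceeds in steps:

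- Intra-class correlations (ICCs) of Cmax are computed "first separately for each of the forms (protonated and free base) and then for all Cmax measurements from the same participant".
- Models of Cmax on flux are fitted within each form. In this step the plan says: "We will use model fit criteria to select the correlation structure and representation of flux concentrations that best describes the data". It names neither the criterion nor the candidate structures.
- For the pooled model, "we will integrate the form effect by using linear mixed models with both concentration and form as predictors as well as an interaction term" is the whole specification. Its stated purpose is "to investigate whether different form-concentration combinations influence Cmax differently".

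The same sequence is applied to dCi/dt, Tmax and AUC. Sections 9.4.1 and 9.4.2 only refer back to this text. The sample size in 9.2 uses a single ICC of 0.4, "which conservatively assumes only modest correlation between Cmax measures within the same participant". No contrast is named for the form hypothesis.

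**The concern.** This is a split-plot layout. Form changes only between a participant's visits; flux changes between bouts within a visit. The form difference averaged over flux therefore rests on 15 paired visit differences (14 df), however many bouts are run. A model with a participant intercept alone judges it against an error term made up mostly of bout-to-bout variation (98 df). If a participant's delivery shifts from day to day for reasons unrelated to form, that shift affects all four bouts of a visit and can be reported as a form effect.

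At stake is one of the two hypotheses in 9.1, and the stated reason for the second visit, on each of the four pharmacokinetic outcomes.

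**Working it through.** **The plan's own figure.** Section 9.2 gives N = 15, alpha 0.05, ICC 0.4, effect size 0.4 and 90% power. The effect-size metric is not named, so I take it as Cohen's f. A repeated-measures F test over four fluxes has noncentrality 0.4² × 15 × 4 / (1 − 0.4) = 16 on 3 and 42 df. Power is 0.908, and 0.884 with 14 participants, so the stated N reproduces. It is the power for the within-visit flux effect and contains no visit-level variance.

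**Inputs for the form effect.** From the documents: 15 participants, 2 visits, 4 bouts per visit (120 values). Assumed: balanced data, normal errors, bout variance 1, participant-by-visit variance r. The documents give no value for r, so a range is shown. In this design r also absorbs any participant-by-form variation, which cannot be separated from visit variation.

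**Formulas.**

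- True variance of the flux-averaged form difference: (2/60)(1 + 4r).
- A participant-only model pools 14 visit-level df with 84 bout-level df. Its residual variance has expectation 1 + (4 × 14/98)r = 1 + 4r/7, so it reports (2/60)(1 + 4r/7).
- The SE is too small by the factor √[(1 + 4r)/(1 + 4r/7)]. At r = 0.25 this is √(2/1.143) = 1.32.

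**Type I error of a nominal 5% test** (1,000,000 draws per r). The participant-only test is F(1, 98). The AIC and BIC columns assume that fit-based selection is carried into the pooled model with a visit effect as a candidate, kept if the REML likelihood ratio exceeds 2 or ln 120 = 4.79.

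| r | SE factor | Participant-only | AIC | BIC | Paired, 14 df |
|---|---|---|---|---|---|
| 0 | 1.00 | 5.0% | 4.7% | 5.0% | 5.0% |
| 0.05 | 1.08 | 6.9% | 6.1% | 6.7% | 5.0% |
| 0.10 | 1.15 | 8.8% | 6.9% | 8.1% | 5.0% |
| 0.25 | 1.32 | 13.8% | 7.2% | 9.8% | 5.0% |
| 0.50 | 1.53 | 19.8% | 6.0% | 8.2% | 5.0% |
| 1.0 | 1.78 | 27% | 5.2% | 5.7% | 5.0% |

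Selection does not fully protect because it often drops the visit effect when it matters. At r = 0.10 and 0.25, AIC keeps it in 27% and 60% of trials, and BIC in 9% and 35%.

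As a check, 300 REML fits with participant, visit and residual variances of 0.40, 0.20 and 0.40 (r = 0.50) gave a form SE of 0.130 with participant only and 0.197 with a visit intercept. The empirical SD was 0.188 and the theoretical value is √[(2/60)(0.40 + 0.80)] = 0.200.

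**Contrasts that are not, or barely, affected** (r = 0.10, 0.25, 0.50, 1.0; type I errors from 60,000 simulated data sets per r):

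- Form at one flux: SE factor √[(1 + r)/(1 + 4r/7)] = 1.02, 1.05, 1.08, 1.13; type I error 5.4, 6.2, 7.0, 8.5%.
- Form by concentration: visit effects cancel, so the participant-only test is conservative, at 4.1, 3.1, 2.1, 0.9%. Flux contrasts are likewise within-visit and not inflated.

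**The case against.** The strongest reply is that this is an omission, not a wrong choice. A reader might infer that the plan commits to a participant-only model and that the form test will therefore run at up to 27% error. The documents do not support that. The plan specifies mixed models, leaves the correlation structure to fit criteria, and gives no visit variance. The 27% needs a participant-only model, an averaged contrast and a ratio of 1.0 together.

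The contrast is also open. The pooled model's declared purpose is the form-by-concentration combinations, where the test is conservative. With the interaction in the model, the form coefficient under reference coding is a single-flux contrast. If flux is continuous and uncentred, it is the contrast at flux zero, with an SE factor of only 1.003 to 1.022 for r from 0.10 to 1.0.

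The plan also contains a diagnostic. With one form per visit, the per-form ICC is a same-visit correlation, and comparing it with the all-measures ICC could reveal visit-level clustering.

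Finally, several controls reduce visit variance: baseline subtraction at each bout and fixed puff duration, interval and number (4.1), the nicotine-free hour before each session (5.3), and device conditioning (6.2.4). The plan adds: "We will also repeat the main analyses adjusting for puffing intensity". If that removed half of a 0.25 ratio (assumed), the participant-only error would be 9.7% instead of 13.8%.

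These points limit the size of the concern but do not close it. The fit-criteria sentence belongs to the per-form step, where each participant normally has one visit. Participant and visit are then aliased, and selection there cannot detect visit variance. The ICC comparison is not linked to the pooled model. The controls do not show that visit variance is zero: the Synopsis has puffing flow rate measured, not fixed, and the intensity adjustment is a repeat analysis. Counter-balancing protects against order bias but does not remove this variance.

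**Conclusion.** The point holds as a conditional gap. If the 9.1 form hypothesis is tested as a flux-averaged difference with participant-only clustering, the test is anti-conservative whenever visit variance is positive: 6.9% at a ratio of 0.05, 13.8% at 0.25 and 27% at 1.0. Fit-based selection, if carried over with a visit term as a candidate, limits this to about 7% (AIC) or 10% (BIC). At a ratio of zero there is no inflation. The ratios are assumptions, and the figures rest on balanced data and normal errors.

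It would be going too far to conclude that the flux analyses or the sample size are undermined. Flux and interaction tests are not inflated, and N = 15 reproduces for the flux effect.

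Severity is between minor and should. The harm is conditional, but it touches a stated hypothesis and the remedy is cheap.

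**What to change.** State in 9.4 that the form hypothesis is tested as the model-based form difference averaged equally over the four fluxes. The model has fixed effects for flux, form and form-by-flux, and random intercepts for participant and for actual visit day within participant. Both intercepts are kept whatever the fit criteria favour, with Kenward-Roger or Satterthwaite df (about 14 for form). Use actual visit day because 4.1 allows an additional day to recollect data. Fit criteria can still choose how flux is represented in the other analyses.

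The model-based average handles a missing bout. A paired comparison of four-flux means should serve only as a check, in participants with all four bouts usable at both visits.

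Apply this to Cmax, dCi/dt, Tmax and per-bout AUC. Section 4.1 can also be read as defining one AUC per visit, running to 160 min across the four bouts. If that is meant, there is no visit effect to estimate, and a paired comparison of the two visits is the right test. The plan should say which AUC it means.

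No new data are needed. The costs, if visit variance is truly zero, are:

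- **Interval width.** The 95% half-width is 2.145 × √(2 × 0.25/15) = 0.39 bout SD on 14 df, against 1.984 × 0.183 = 0.36 on 98 df, about 8% wider. At r = 0.25 it is 0.55 against 0.39, but there the narrower interval is too narrow.
- **Conservatism.** With the visit variance constrained to be non-negative, the mixed model's type I error is about 3% (2.8 to 3.6%, depending on the df used when the estimate is zero).
- **Power.** For an illustrative form difference of 0.4 total SD at ICC 0.4, the SE is √(2 × 0.6/60) = 0.141. Power is about 75% on 14 df against 80% on 98 df.

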#### **9.4.1 General Approach**

As above.

#### **9.4.2 Analysis of the Primary Efficacy Endpoint(s)**

As above.

#### **9.4.3 Analysis of the Secondary Endpoint(s)**

N/A

#### **9.4.4 Safety Analyses**

Safety events will be analyzed descriptively in aggregate.

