**Accrual Ceiling**

15 subjects (excluding those lost to follow up or disenrolled)

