**Description of Study Intervention**

Aim1 study design and method. The purpose of Aim1 at YSM is to examine the influence of nicotine flux, and nicotine form, on the rate and dose of nicotine delivery obtained from arterial blood measurements. This study involves a 4 x 2 crossover experimental design of four nicotine fluxes: 9, 18, 27, 35 µg/sec, and two nicotine forms (i.e., free-base and protonated). These nicotine fluxes are within the range reported for ENDS (3.1-111µg/sec) (El Hourani, 2022). Also, in Aim1, we will isolate the effect of form on the pharmacokinetics of nicotine delivery by controlling for puffing behavior. We will hold puff topography constant by controlling puff duration, inter-puff interval, and number of puffs using the LabVape PTL and confirm the data using eTop.

The flux/form conditions will be tested by participants in two lab visits separated by one to four weeks to minimize carryover effects. All sessions will be double-blinded. In the first visit, participants will use the ENDS device with one nicotine form and four fluxes in random order. Participants will be instructed to attend the lab for a second visit, to test the four fluxes but with the other nicotine form. The second visit will allow us to isolate the effect of nicotine form on nicotine delivery. The order of nicotine form in the two visits will be counter-balanced across participants. Outcome measures include arterial blood nicotine delivery, and puff topography. Below we provide the methodological details on device/liquid selection, preparation, flux validation, clinical lab procedures, and data analysis. Participants will be instructed to use the **Subox mini C ENDS device connected to the LabVape PTL (which limits puff duration to 3 seconds)** in four bouts separated by a 60min resting period. The e-liquids vaped are as follows: Propylene glycol(PG)/Glycerol (VG), 30/70 ratio by volume. Nicotine at different concentrations: (2, 4, 7 and 10mg/mL) Benzoic acid: ~1:1 molar ratio with nicotine. All these ingredients will be used to prepare the needed e-liquids to conduct the study. For more details, please review the ITP application.

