### 7.2 Participant Discontinuation/Withdrawal from the Study

Participants are free to withdraw from participation in the study at any time upon request.

An investigator may discontinue or withdraw a participant from the study for the following reasons:

- Pregnancy
- Significant study intervention non-compliance
- If any clinical adverse event (AE), laboratory abnormality, or other medical condition or situation occurs such that continued participation in the study would not be in the best interest of the participant
- Disease progression which requires discontinuation of the study intervention
- If the participant meets an exclusion criterion (either newly developed or not previously recognized) that precludes further study participation
- Participant unable to receive the study intervention> for 4 weeks.

The reason for participant discontinuation or withdrawal from the study will be recorded in the database. Subjects who sign the informed consent form and are randomized but do not receive the study intervention may be replaced. Subjects who sign the informed consent form, and are randomized and receive the study intervention, and subsequently withdraw, or are withdrawn or discontinued from the study, may be replaced.

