### 8.2 Safety and Other Assessments

Safety will be assessed at each stage of the study by the RA and RN using the health assessments checklist. There will be ongoing review by the PI and study physician with positive findings of a change in symptom or single severe symptom triggering clinical referral to treating physician or ED. The RA will ensure that the enrolled study subjects are eligible and sign informed consent. The study RN will be present with the study subject during all procedures, and the study subject's vital signs (HR, BP) will be measured by continuous monitoring. Any adverse events will be documented as described below.

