#### **10.1.5 Safety Oversight**

Safety oversight will be under the direction of a Data and Safety Monitoring Board (DSMB) composed of individuals with the appropriate expertise, including nicotine and tobacco use. Members of the DSMB should be independent from the study conduct and free of conflict of interest, or measures should be in place to minimize perceived conflict of interest. The DSMB will meet at least yearly to assess safety and efficacy data on each arm of the study. The DSMB will operate under the rules of an approved charter that will be written and reviewed at the organizational meeting of the DSMB. At this time, each data element that the DSMB needs to assess will be clearly defined. The DSMB will provide its input to the study investigators.

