#### **Data and Safety Monitoring Board (DSMB)**

The Yale TCORS has previously established a DSMB to provide the highest protection for study participants. Given the close collaboration and overlapping safety concerns between Aim 1 of the proposed study and those currently being conducted by TCORS, we will utilize the existing DSMB for the proposed study. The composition of the DSMB has been constructed following NIH guidelines and includes the following members who also served on the DSMB in TCORS-1:

Member	Affiliation	Role
[name]	[name], U. of Toronto	DSMB Chair
[name]	Assoc. [name], Columbia U.	Statistician
[name]	[name], U. South FL	Content Expert

**Procedures:** The Core, in collaboration with the PIs, will prepare twice yearly DSMB reports, which include information on enrollment, participant retention rates and adverse events, and preliminary analyses as appropriate. The DSMB oversees an initial protocol

review and then ongoing reviews. These reports are supplemented by rapid notification of all studies' serious adverse events. The PIs will meet with the DSMB to review each study. The DSMB will meet initially in an open session, attended by the PIs. Then, a closed session is held in which the DSMB Chair conducts a review of all issues and puts these to vote. The purview of the DSMB includes, but is not limited to, assessments of data quality and timeliness, participant recruitment, subject retention, safety and efficacy data, and protocol compliance. The DSMB also considers advances occurring elsewhere and their impact on the potential risks and benefits of the study. Following the DSMB meeting, a report of the meeting, including recommendations will be prepared and submitted to the PIs, to the IRBs, and to the funding agency.

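### The final safety analysis commits to no breakdown by nicotine form or flux, although the DSMB is to review safety by an undefined arm

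*Combined protocol and SAP*

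**What the plan says.** The safety analysis in section 9.4.4 reads, in full: "Safety events will be analyzed descriptively in aggregate". No other part of the statistical section adds a split. Sections 9.4.7 (sub-groups), 9.4.8 (individual tabulation) and 9.4.9 (exploratory) are marked not applicable, and the models in section 9.4 cover the pharmacokinetic outcomes and puffing.

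On oversight, section 10.1.5 states: "The DSMB will meet at least yearly to assess safety and efficacy data on each arm of the study". It leaves the data elements to a charter. The DSMB procedures describe twice-yearly reports "which include information on enrollment, participant retention rates and adverse events, and preliminary analyses as appropriate", without saying whether events are shown by condition.

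The conditions are "four nicotine fluxes: 9, 18, 27, 35 µg/sec, and two nicotine forms (i.e., free-base and protonated". Section 6.3 gives one form per visit, with visits one to four weeks apart. Section 6.1.2 puts the four flux bouts of a visit one hour apart. Section 8.3.4 has each adverse event recorded with onset time, severity, relationship and resolution. Section 8.2 adds that "vital signs (HR, BP) will be measured by continuous monitoring".

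**The concern.** The trial exists to inform regulation by nicotine flux and form, and it hypothesises higher delivery with the protonated form. Delivery is to be modelled by flux, form and their interaction, yet safety is to be summarised by neither. In a crossover the informative comparison is within the person, form against form and bout against bout, and a pooled summary does not show it. A pooled count may also mix product effects with the arterial-line effects listed in section 2.3.1 (pain, hematoma, bruising), which belong to the cannulation.

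The two sections also do not meet. One promises a pooled summary. The other expects data by arm in a design where each participant is due to pass through every condition. Whoever prepares the tables has no rule for assigning an event to a condition, and no denominator.

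**Working it through.** The plan gives no figure for the safety analysis, so there is none to reproduce. The sample size in section 9.2 concerns Cmax and is not affected.

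**1. Number of conditions.** 4 fluxes × 2 forms = 8. With 15 participants completing both visits and no repeats, 15 × 8 = 120 bouts.

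**2. Range of nominal emission.** Section 4.1 gives three 3-second puffs per bout, so 3 × 3 = 9 s of puffing. Emission per bout = flux × 9 s:

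| Flux (µg/sec) | Emission per bout (µg) |
|---|---|
| 9 | 81 |
| 18 | 162 |
| 27 | 243 |
| 35 | 315 |

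The ratio is 315/81 = 3.9. A completed visit totals 81 + 162 + 243 + 315 = 801 µg, whatever the flux order or form. The 3.9-fold contrast therefore exists between bouts only; the two forms are compared at equal nominal emission.

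**3. What a pooled summary leaves out.** As an illustration (assumption), let three events occur in one condition, in three different participants.
- By condition: 3/15 = 20% in that cell.
- Pooled by bout: 3/120 = 2.5%.
- Pooled by participant: 3/15 = 20%, with nothing to show which form or flux was involved.

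**4. What the recorded data can support.** Visits are at least a week apart, so an event can be placed with a visit and hence a form. Flux is harder. The four fluxes are given about an hour apart on one day, while section 8.3.4 collects events until 7 days (non-serious) or 30 days (serious) after the last day of participation. Only an event that starts between one bout and the next can reasonably be placed with a flux. The fourth bout has no following bout, so its window needs a stated end.

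**5. What the tables could show.** With 0 events in 15, the one-sided 95% upper bound is 1 − 0.05^(1/15) = 18.1%. The chance of at least one event in a cell, 1 − (1 − p)^15, is 54%, 79% and 96% at assumed true rates of 5%, 10% and 20%. A paired exact (McNemar) comparison of two conditions needs at least 6 discordant pairs against 0 for two-sided p below 0.05: 5 against 0 gives 2 × 0.5^5 = 0.0625, and 6 against 0 gives 2 × 0.5^6 = 0.031. Its power at n = 15 is 16% for assumed rates of 5% and 30%, and 49% for 10% and 50%, taking responses as independent. Formal testing is not worthwhile; description is.

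**The case against.** The strongest case on the other side is that this is one unspecified table, not a loss of information. Much of that stands. A nurse is present throughout, bouts are directed and observed, and the PI reviews safety data after every test day. A reader might infer that harm related to form or flux would be concealed. The documents do not support that, because an in-session event can be traced to its bout from the records.

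A reader might also infer that section 9.4.4 prevents the DSMB from reviewing by arm. It does not. DSMB review is a separate process, its charter is to define what it sees, and serious events are notified rapidly. What remains is that *arm* has no definition and no section commits anyone to supply data in that form.

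A third tempting inference is that safety would be counted only in the 15 completers. The accrual ceiling is "15 subjects (excluding those lost to follow up or disenrolled", and section 7.2 says that treated participants who stop, "and subsequently withdraw, or are withdrawn or discontinued from the study, may be replaced". These are recruitment rules. Nothing restricts the safety summary to completers, section 8.3.4 requires all on-study events to be documented, and any percentage of exposed participants omitted would rest on an invented exclusion. It is fair only to say that the denominator is unstated; section 9.3 names e-cigarette users and no more.

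Two further points hold. The pooled wording might mean summed over participants, although pooling over conditions is its natural reading. And safety by flux is not a stated objective: heart rate and blood pressure appear as monitoring, not as outcomes, and the documents do not say that readings are stored by bout.

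**Conclusion.** The point holds as a gap in planned analysis and reporting. If the plan is followed as written, eight conditions spanning a nominal 3.9-fold range of emission per bout yield one safety summary, with no account by form or flux, although onset times and visit spacing would allow one. Sections 9.4.4 and 10.1.5 need to be reconciled.

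This rests on reading the pooled wording as covering conditions, and on nominal flux and puff duration being achieved. It does not touch the primary pharmacokinetic result or the sample size. Attribution has a limit that no table removes: events after a visit can be placed with a form, not a flux.

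**What to change.** Rewrite section 9.4.4 and align section 10.1.5 with it:

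- Define *arm* as form (visit) and form by flux (bout).
- Define the safety population as all participants who had a line placed or took a puff, including replaced participants, repeat bouts and third visits.
- Tabulate adverse events by form, giving both participants and bouts as denominators.
- Tabulate by flux only those events with onset from the start of a bout to the start of the next, and state when the window for the fourth bout ends.
- List arterial-line events separately, per cannulation.
- Give the DSMB the same tables, coded if the blind is to be kept.
- Summarise heart rate and blood pressure by condition only if the monitored readings are stored at bout level.

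The cost is a paragraph of wording and a few descriptive tables. The adverse-event tables need no new data collection. The price is sparse cells of about 15 participants, so the text should say that the tables are descriptive and that no test is planned.
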